2.7.2.3 Parasite clearance time (PCT) and fever clearance time (FCT)

Descriptive statistics (mean, standard error, median, quartiles) will be presented for each treatment by cohort using the Kaplan-Meier method based on the FAS. Kaplan-Meier curves will be provided.

Parasite clearance time

PCT will be calculated based on uncorrected parasite counts. Patients without parasite clearance for whatever reason will be censored at the time of last parasite assessment.

Fever clearance time

Patients who had no fever at pre-dose will not be included in the analysis of FCT. Patients without fever clearance for whatever reason will be censored at the time of last temperature assessment.

Handling of missing values/censoring/discontinuations

In case that a patient receives rescue medication before (parasite or fever) clearance, the time to event will be censored at the first use of rescue medication.

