6.2.3 Rescue medication

The following circumstances warrant discontinuation of study treatment (during the treatment period) and the implementation of rescue medication by the investigator (Commencement of rescue medication may occur after the start of study drug and up to Day 43):

Early Treatment Failure (ETF)

- Development of danger signs or severe malaria on Day 2, Day 3, Day 4 in the presence of parasitemia.
- Parasitemia on Day 3 higher than Day 1 count irrespective of axillary temperature.
- Parasitemia on Day 4 with axillary temperature $\geq 37.5^\circ$.
- Parasitemia on Day 4 equals to or more than 25% of count on Day 1.

Late Clinical Failure (LCF)

- Development of danger signs or severe malaria on any day from Day 5 to Day 43 in the presence of parasitemia without previously meeting any of the criteria of Early Treatment Failure.
- Presence of parasitemia and axillary temperature $\geq 37.5^\circ$ on any day from Day 5 to Day 43 without previously meeting any of the criteria of Early Treatment Failure.

Late Parasitological Failure (LPF)

- Presence of parasitemia on any day from Day 8 to Day 43 and axillary temperature $< 37.5^\circ$ without previously meeting any of the criteria of Early Treatment Failure or Late Clinical Failure.

Rescue treatment involves therapy with an effective antimalarial available locally as per local medical practice or National Treatment Guidelines. Administration may be oral or parenteral depending on the subject's clinical condition. Rescue treatment will not be considered study medication. The exact rescue regimen and route of administration must be recorded on the appropriate CRF.

Patients will be monitored, either in clinic, or via home visits for the duration of treatment to ensure adherence to the rescue medication therapy. These patients will not discontinue the study (i.e., all the examinations as per the assessment schedule and all CRF for this patient will need to be completed), and they will not be replaced (unless the PK data cannot be properly analyzed due to treatment schedule discontinuation).

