2.1.1.1 Clearance and treatment failure definitions

Fever Clearance time (FCT), defined as time from the first dose until the first time the axillary body temperature decreased below and remained below 37.5°C axillary or 38.0°C oral/tympanic/rectal for at least a further 24 hours. Note: 38.0°C is the temperature threshold for fever using oral/tympanic/rectal, which will be also used in the treatment failure definition.

Parasite clearance time (PCT), defined as time from the first dose until the first total and continued disappearance of asexual parasite forms which remained at least a further 48 hours.

Early Treatment Failure (ETF)

- Development of danger signs or severe malaria on Day 2, Day 3, Day 4 in the presence of parasitaemia.

- Parasitaemia on Day 3 higher than Day 1 count irrespective of axillary temperature.
- Parasitaemia on Day 4 with axillary temperature $\geq 37.5^\circ$.
- Parasitaemia on Day 4 equals to or more than 25% of count on Day 1.

Late Clinical Failure (LCF)

- Development of danger signs or severe malaria on any day from Day 5 to Day 43 in the presence of parasitaemia without previously meeting any of the criteria of Early Treatment Failure.
- Presence of parasitaemia and axillary temperature $\geq 37.5^\circ$ on any day from Day 5 to Day 43 without previously meeting any of the criteria of Early Treatment Failure.

Late Parasitological Failure (LPF)

- Presence of parasitaemia on any day from Day 8 to Day 43 and axillary temperature $<37.5^\circ$ without previously meeting any of the criteria of Early Treatment Failure or Late Clinical Failure.

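### Censoring parasite clearance time at rescue is informative, because every early-failure trigger for rescue requires parasites still present; the Kaplan-Meier curve can then overstate the proportion cleared

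*SAP*

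**What the plan says.** PCT and FCT are secondary efficacy endpoints. SAP 2.7.2.3 gives the estimator: "Descriptive statistics (mean, standard error, median, quartiles) will be presented for each treatment by cohort using the Kaplan-Meier method based on the FAS". Curves are also planned. Two censoring rules apply to PCT:

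- No clearance: "Patients without parasite clearance for whatever reason will be censored at the time of last parasite assessment".
- Rescue before clearance: "the time to event will be censored at the first use of rescue medication". Protocol 12.5.1 has the same rule.

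SAP 2.1.1.1 defines PCT as "time from the first dose until the first total and continued disappearance of asexual parasite forms which remained at least a further 48 hours". FCT requires that the temperature "remained below 37.5°C axillary or 38.0°C oral/tympanic/rectal for at least a further 24 hours".

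Protocol 6.2.3 links rescue to treatment failure: "The following circumstances warrant discontinuation of study treatment (during the treatment period) and the implementation of rescue medication by the investigator". The list that follows is the set of failure criteria. Examples from the early-failure group are "Development of danger signs or severe malaria on Day 2, Day 3, Day 4 in the presence of parasitemia" and, in the SAP's wording, "Parasitaemia on Day 4 equals to or more than 25% of count on Day 1". The same protocol section keeps rescued infants in the study with all scheduled examinations. Protocol 6.5.2 and 6.7.2 add a separate route to rescue: a repeat dose that is itself vomited within an hour.

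**The concern.** Kaplan-Meier censoring assumes that a censored infant would have gone on to clear at the same rate as those still being followed. That is hard to defend when the infant was censored because it met a failure criterion that needs parasites to be present. The estimator passes the censored infant's weight to those who clear later, so non-clearance on study drug can vanish from the end of the curve.

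This matters here because the protocol gives artemether the job of early parasite reduction (1.1), and the starting artemether dose was chosen to be conservative (4.2). Slow or absent clearance is one of the results that would bear on whether exposure is sufficient, and PCT is the endpoint that describes it.

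**Working it through.** **Inputs from the documents.** About 22 infants per cohort (SAP 3.1.2). Blood films at 8, 24, 36, 48, 60, 72, 96 and 168 h, with Day 2 starting at 24 h, Day 3 at 48 h and Day 4 at 72 h (protocol Table 8-1). The plan's cohort size reproduces: 16 / (1 − 0.25) = 21.3, rounded up to 22. The documents give no expected PCT, FCT or number of rescues. Every rescue count and clearance time below is therefore an assumption, and a range is shown.

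**Step 1: what triggers rescue.**

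| Trigger | Requires parasitaemia | Requires fever |
|---|---|---|
| Early failure: danger signs or severe malaria, Days 2–4 | yes | no |
| Early failure: Day 3 count above Day 1 | yes | no |
| Early failure: Day 4 parasitaemia with fever | yes | yes |
| Early failure: Day 4 count at least a quarter of Day 1 | yes | no |
| Repeat dose vomited | no | no |

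The late-failure criteria in protocol 6.2.3 also require parasitaemia. For PCT, failure-triggered rescue is thus tied to non-clearance. For FCT, one early-failure criterion of four is tied to fever.

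**Step 2: the estimator.** S(t) is the product over clearance times of (1 − d/r), with d clearing and r at risk; the proportion cleared is 1 − S(t). Two rules are compared: (a) as written, rescued infants leave the risk set at rescue; (b) they stay in it as not cleared. With no other censoring, (b) equals the cumulative incidence of clearance with rescue as a competing event.

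**Step 3: rescue at the Day 4 film.** Assume 22 infants: 5, 7, 4 and 2 clear at 24, 36, 48 and 60 h, 2 are rescued at 72 h and 2 clear at 96 h. By 60 h, 18/22 = 81.8% have cleared under both rules. At 96 h:

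- (a) r = 2, d = 2, so S = 0 and the curve ends at 100%.
- (b) r = 4, d = 2, so S = 4/22 × 2/4 = 2/22 and the curve ends at 90.9%.

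Clearance at 96 h is possible without rescue. An afebrile infant with no danger signs and a Day 4 count below a quarter of Day 1 (and a Day 3 count not above Day 1) meets no early-failure criterion.

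| Rescued uncleared, of 22 | Final level, as written | Kept as not cleared |
|---|---|---|
| 1 at 72 h, last clearance 96 h | 100% | 95.5% |
| 2 at 72 h, last clearance 96 h | 100% | 90.9% |
| 4 at 72 h, last clearance 96 h | 100% | 81.8% |
| 11 at 72 h, last clearance 96 h | 100% | 50.0% |
| 2 at 48 h, last clearance 60 h | 100% | 90.9% |
| 2 at 72 h, last clearance 60 h | 90.9% | 90.9% |

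The last row shows the condition: with no clearance after the last rescue, the two rules give the same curve. With 1, 2 or 4 rescued at 72 h, the median and quartiles are identical under both rules. With 11 rescued, the upper quartile is 96 h as written and not reached under (b).

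**Step 4: earlier rescues, and the mean.** Assume 4, 6, 5, 3 and 1 infants clear at 24, 36, 48, 60 and 72 h, two are rescued at 30 h and one just after the 60 h film.

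| Time (h) | S as written | S, rescued kept |
|---|---|---|
| 24 | 18/22 = 0.818 | 18/22 = 0.818 |
| 36 | × 10/16 = 0.511 | 12/22 = 0.545 |
| 48 | × 5/10 = 0.256 | 7/22 = 0.318 |
| 60 | × 2/5 = 0.102 | 4/22 = 0.182 |
| 72 | × 0/1 = 0 | 3/22 = 0.136 |

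Quartiles are 36, 48 and 60 h under both rules. The mean is the area under S:

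- As written: 24 + 12 × (0.818 + 0.511 + 0.256 + 0.102) = 44.25 h.
- Rescued kept, to 72 h: 24 + 12 × 41/22 = 46.4 h.
- Rescued kept, to 168 h: 46.36 + 96 × 3/22 = 59.5 h.

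Most of the shift in the mean therefore depends on where it is truncated, which the SAP does not state.

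**The case against.** The strongest reply is that these infants are not lost from the efficacy results. SAP 2.7.2.1 counts rescue for *P. falciparum* as treatment failure, uncorrected ACPR is reported on the FAS from Day 8, and the FAS Kaplan-Meier analysis in 2.7.2.1.1 has treatment failure as its event. The DMC also sees efficacy and safety data at each check. This stands. A reader might infer that the censoring rule conceals early failures from the trial; the documents do not support that. The reply does not repair the clearance outputs, though, because ACPR does not describe how fast or in what proportion infants clear. Nor is every other analysis a backstop. An infant rescued before the 48 h dose has had at most 4 of 6 doses (67%) and falls below the 80% needed for the per-protocol set, and the recrudescence analysis is limited to infants who cleared by Day 7.

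Three further limits stand:

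- The distortion needs a later clearance. If the three rescues in Step 4 all fall just after the 72 h film, S(72 h) = 4/22 × 3/4 = 13.6% under both rules.
- Rescue at 30 h can only come from danger signs or severe malaria with parasitaemia, among the early-failure triggers. In Step 4, 18 of 22 infants are still uncleared then, so that example shows non-clearance as a condition of rescue and not as what singles the infant out. The Day 3 and Day 4 count criteria are the cleaner case.
- A reader might infer that FCT is affected to the same degree. It is not: fever without parasites triggers no rescue under the failure criteria, and infants without pre-dose fever are excluded from FCT.

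**Conclusion.** The point holds for PCT as a matter of the stated rules: the plan treats as non-informative a censoring event that, for failure-triggered rescue, requires the outcome not to have occurred. The size is conditional. It is nil if no infant is rescued before clearance or if none clears afterwards. Otherwise, in a cohort of 22 with no other censoring and the last clearance after the last rescue, the curve ends at 100% and overstates final clearance by 1/22 = 4.5 percentage points per rescued infant. The tail changes, and the mean can change by an amount that depends on its truncation. The median and quartiles did not move with 1 to 4 infants rescued, so it would be wrong to infer that the median clearance time is materially biased. For FCT the same argument applies only to infants still febrile at a failure-triggered rescue.

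These are descriptive secondary endpoints without hypotheses, and the primary PK result is untouched. The change is worth making before database lock because the affected curves and means are planned outputs and the correction uses data already collected.

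**What to change.** In SAP 2.7.2.3, with protocol 12.5.1 aligned or the departure recorded in SAP section 4:

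1. In the main PCT analysis, treat rescue for treatment failure before clearance as a competing event. Alternatively, keep these infants in the risk set as not cleared, to the same end of follow-up as unrescued non-clearers; the two agree when there is no other censoring. Parasite disappearance after rescue should not count as clearance on study drug.
2. Report the number and percent rescued before clearance, and the proportion cleared by 24, 48 and 72 h with failure-triggered rescues counted as not cleared.
3. Continue to censor infants rescued only because a repeat dose was vomited.
4. For FCT, apply the same handling to infants still febrile at failure-triggered rescue.
5. State the time to which any mean is restricted.
6. Keep the present rule as a sensitivity analysis.

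No clinical rule and no data collection changes, since rescued infants already stay in scheduled follow-up. The cost is a few sentences, one extra table and possibly slightly less favourable clearance figures.

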2.8 Safety analyses

For all safety analyses, the safety set will be used. All listings and tables will be presented by cohort and treatment group.

Safety summaries (tables, figures) include only data from the core period (up to Day 43) with the exception of baseline data which will also be summarized where appropriate (e.g. change from baseline summaries). In particular, summary tables for adverse events (AEs) will include only the core period events, with a start date during that period.

2.8.1 Adverse events (AEs)

A treatment-emergent AE is defined as any AE that develops after initiation of the study treatments or any event already present that worsens following exposure to the study treatment.

Adverse events will be summarized by presenting, for each cohort and treatment group, the number and percentage of patients having at least one AE, having an AE in each primary system organ class and having each individual AE (preferred term).

For summaries by maximum severity the following applies: if a patient reported more than one adverse event with the same preferred term, the adverse event with the greatest severity will be presented. If a patient reported more than one adverse event within the same primary system organ class, the patient will be counted only once with the greatest severity at the system organ class level.

The MedDRA version used for reporting the adverse events will be described in a footnote.

All information obtained on adverse events will be listed by cohort, treatment group, and subject.

The number and percentage of subjects with treatment emergent adverse events will be summarized in the following ways:

- by cohort, treatment group, primary system organ class and preferred term.
- by cohort, treatment group, primary system organ class, preferred term and maximum severity.
- by cohort, treatment group, Standardized MedDRA Query (SMQ) and preferred term.

Additionally the number and percentage of patients will be presented for the following summaries:

- AEs related to study medication.
- Deaths.
- Serious adverse events.
- AEs leading to discontinuation of study treatment.
- AEs leading to dose adjustment.

These summaries will be presented by cohort, treatment group, primary system organ class and preferred term.

For the legal requirements of ClinicalTrials.gov and EudraCT, two required tables on treatment emergent adverse events which are not serious adverse events with an incidence greater than 5% and on treatment emergent serious adverse events and SAE suspected to be related to study treatment will be provided by primary system organ class and preferred term on the safety set.

If for a same patient, several consecutive AEs (irrespective of study treatment causality, seriousness and severity) occurred with the same SOC and PT:

- a single occurrence will be counted if there is ≤ 1 day gap between the end date of the preceding AE and the start date of the consecutive AE
- more than one occurrence will be counted if there is > 1 day gap between the end date of the preceding AE and the start date of the consecutive AE

For occurrence, the presence of at least one SAE / SAE suspected to be related to study treatment / non-SAE has to be checked in a block e.g., among AE's in a ≤ 1 day gap block, if at least one SAE is occurring, then one occurrence is calculated for that SAE.

2.8.1.1 Adverse events of special interest / grouping of AEs

The number (and proportion) of subjects with adverse events of special interest/related to identified and potential risks will be summarized by risk name, PT, cohort and treatment group.

Risk names will be sorted alphabetically, and, within each risk name, the PTs will be sorted in descending order of frequency. If a patient reported more than one adverse event with the same PT, the AE will be counted only once. If a patient reported more than one AE within the same risk, the patient will be counted only once at that risk.

The adverse events of special interest are defined in the Case retrieval Sheet (CRS) which is updated for each MedDRA dictionary.

2.8.2 Laboratory data

All laboratory data will be listed by cohort, treatment group, subject, and visit/time and if normal ranges are available abnormalities will be flagged. Notable values will be flagged as well.

Descriptive statistics will be generated for all clinical laboratory tests performed (actual values and changes from baseline) for two groups of laboratory tests (hematology and blood chemistry) by laboratory test, cohort, treatment group and visit/time. Change from baseline will only be summarized for patients with both baseline and post baseline values and will be calculated as:

change from baseline = post baseline value – baseline value.

The following laboratory parameters will be analyzed for hematology test group: hemoglobin, platelets, white blood cell count, Reticulocytes, hematocrit, red blood cell (RBC) count, lymphocytes, lymphocytes (%), monocytes, monocytes (%), eosinophils, eosinophils (%), neutrophils, neutrophils (%), basophils, basophils (%), bands, bands (%), differential other and differential other (%).

The following laboratory parameters will be analyzed for blood chemistry test group: sodium, potassium, magnesium, glucose, creatinine, aspartate aminotransferase (AST), alanine aminotransferase (ALT), total bilirubin.

Shift tables using the low/normal/high/ (low and high) classification will be used to compare baseline to the worst value within the core period. The direction of interest for worst value within core period for each laboratory parameter is given in [Table 5-3](#).

2.8.3 Other safety data

2.8.3.1 Vital signs

All vital signs data will be listed by cohort, treatment group, subject, and visit/time and if ranges are available, clinically notable abnormalities will be flagged.

The following quantitative variables will be summarized: Temperature (°C), Pulse (beats/min), Systolic blood pressure (mmHg) and Diastolic blood pressure (mmHg).

Analysis in vital sign measurements using descriptive summary statistics for the actual value and change from baseline will be performed by vital sign, cohort, treatment group and visit/time. Change from baseline will only be summarized for patients with both baseline and post-baseline values and will be calculated as:

Change from baseline = post-baseline value – baseline value.

2.8.3.2 Weights and heights

Weight (g) and Height (cm) will be summarized using descriptive summary statistics for the actual value and the change from baseline by cohort, treatment group and visit/time. For presentation of change from baseline the same rules as stated for vital signs do apply.

All weight and height data will be listed by cohort, treatment group, subject, and visit/time.

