2.1 Data analysis general information

Data will be analyzed by [REDACTED] on behalf of Novartis after the final DBL using SAS version 9.4 according to the data analysis presented in Section 12 of the study protocol which will also be available in [Appendix 16.1.1 of the CSR](#). Important information is given in the following sections and details will be provided, as applicable, in [Appendix 16.1.9 of the CSR](#).

There will be two planned interim assessments, one after Cohort 1, the second one after Cohort 2. More details can be found in [Section 2.12](#).

Data analyses required for the interim assessments will also be analyzed by [REDACTED] and corresponding outputs will be provided to the DMC. Outputs for the DMC will be part of the CSR shell document. No separate SAP or TFL shell document will be prepared.

After the first 9 patients in Cohort 1 and the first 3 and 9 patients in the higher age subgroup of Cohort 2 (1-28 days) and after the first 3 patients in the 2 younger subgroups of Cohort 2 (if they are recruited) have been treated with the same dose and followed up for at least 2 weeks (and optionally once 9 patients from the age group 15-28 days have completed Day 15), the database will be cleaned reasonably, data management reports using the raw data will be used for the regular review meetings and PK summaries will be generated by Novartis PK scientist.

Statistical analyses will be performed by cohort and treatment group. If there are treatment groups that are used for multiple cohorts, descriptive statistics will be calculated for these treatment groups by pooling data from all cohorts for the primary and key secondary endpoints.

Unless otherwise stated, summary tables/figures/listings will be on all patients included in the population under consideration.

Categorical data will be summarized as frequencies and percentages. For continuous data mean, standard deviation, median, minimum, and maximum will be presented. For selected parameters, the 25th and 75th percentile will also be presented.

There is no stratification done in this study.

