2.2.1 Subgroup of interest

Not applicable.

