5.2 Visit windows

When visit windows are used, all visits will be re-aligned, i.e., they will be mapped into one of the visit windows. E.g., if the Day 4 visit of a patient is delayed and occurs on Day 7, say, it will be re-aligned to visit window Day 8. In the case of major deviations from the visit schedule, or due to unscheduled visits, several assessments of a patient may fall in a particular visit window (either scheduled or unscheduled). Statistical approaches to handle multiple assessments in a given visit window are specified below.

- The following rules are used to determine the window for other visits post baseline:
 - “Lower limit” = “upper limit of prior applicable visit” + 1
 - “Upper limit” = “target day of current visit” + integer part of (“target day of next applicable visit” – “target day of current visit”)/2 with the exception of Day 43
 - Upper limit for analysis visit Day 43 is day 50

Based on the different assessments [Table 5-1](#) describes the analysis visit window mapping. Repeat and/or unscheduled visits (which will be numbered in the database according to new NCDS standards) will be mapped for analysis purposes in the same way. If there are multiple measurements within an analysis window, the conventions defined in [Table 5-2](#) will be used to determine the appropriate measurement to be selected for analysis.

The mapped visits will be used in the by visit analyses. However, the listings will show the collected data regardless of used in the by visit analyses.

Table 5-1 Analysis visit windows based on study day and time

Analysis Visit	Analysis timepoint	Vital signs	Weight/Height	Blood chemistry/ Hematology	Malaria blood film
Baseline	<0 h	up to 0 h	up to 0 h	up to 0 h	up to 0 h
Day 1	8 h	>0 to 16 h	-	-	>0 to 16 h

Day 2	24 h	>16 to 30 h	> 0 to 36 h	> 0 hrs to 42 h	>16 to 30 h
	36 h	>30 to 42 h	-	-	>30 to 42 h
Day 3	48 h	>42 to 54 h	> 36 to 60 h	-	>42 to 54 h
	60 h	>54 to 66 h	-	> 42 to 114 h	>54 to 66 h
Day 4	72 h	>66 to 84 h	>60 to 84 h	-	>66 to 84 h
Day 5	96 h	> 84 to 132 h	> 84 to 132 h	-	> 84 to 132 h
Day 8	168 h	> 132 h to Day 11	> 132 h to Day 11	> 114 h to Day 11	> 132 h to Day 11
Day 15	NA	Day 12 – 22	Day 12 – 22	Day 12 – 29	Day 12 – 22
Day 29	NA	Day 23 – 36	Day 23 – 36	-	Day 23 – 36
Day 43	NA	Day 37 - 50	Day 37 – 50	Day 30 – 50	Day 37 - 50
Age 365 days	NA	-	Aged between 335 – 395 days	-	-

Table 5-2 Rules for flagging variables

Timing of measurement	Type of data	Rule

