5.5 Vital signs and Laboratory – definition of clinically notable values

The following two tables show the clinical notable criteria for vital signs. Clinically notable ranges for laboratory parameters will be defined as values graded or worse 3 (see Table 5-6) using the Division of AIDS (DAIDS) Table for Grading the Severity of Adult and Pediatric Adverse Events (Corrected version 2.1, July 2017).

Table 5-4 Normal Vital Signs according to Age

Values below the lower limit or above the upper limit of normal will be listed as Abnormal.

Age	Heart Rate (beats/min)	Blood Pressure (mm Hg)		Respiratory Rate (breaths/min)
		Systolic	Diastolic	
0-<3 months	100-150*	65-85	45-55	35-55
3-<6 months	90-120	70-90	50-65	30-45
6-12 months	80-120	80-100	55-65	25-40

Reference: [Kliegman et al 2007](#).

* In sleep, infant heart rates may drop significantly lower, but if perfusion is maintained, no intervention is required

For information only, Premature : Heart rate (beats/min): 120-170*; Blood pressure (mm Hg): 55-75/35-45; Respiratory rate (breaths/min): 40-70

Table 5-5 Normal body temperature

Vital sign parameter	Normal range
Oral/Tympanic/rectal body temperature (°C)	>= 37.0 and <= 37.9
Axillary body temperature (°C)	>= 36.5 and <= 37.4

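### Core-period weight and length are summarised only as raw values and raw change, so the sign of the mean change does not show whether infants keep up with expected growth

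*SAP*

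**What the plan says.** SAP 2.8.3.2 covers body weight in grams and length in centimetres. The plan for both is that they "will be summarized using descriptive summary statistics for the actual value and the change from baseline by cohort, treatment group and visit/time". It adopts the change rule of SAP 2.8.3.1: "Change from baseline = post-baseline value – baseline value". All values are also listed by subject. The counterpart, Protocol 12.5.2, plans listings and summary statistics and names no growth reference.

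Other parts of the plan bear on how this table can be read:

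- **No control.** SAP 2.1.1 notes that the study has one arm and no control treatment.
- **No split by age or sex within cohort.** SAP 2.1 says "There is no stratification done in this study", and SAP 2.2.1, "Subgroup of interest", is marked as not applicable.
- **Visit windows.** In SAP Table 5-1 the weight/height windows are Days 23 to 36 for Day 29 and Days 37 to 50 for Day 43. The text of SAP 5.2 confirms the latter: "Upper limit for analysis visit Day 43 is day 50".
- **Scope.** SAP 2.8 limits safety summaries to the core period, up to Day 43.
- **References used elsewhere.** For vital signs, "if ranges are available, clinically notable abnormalities will be flagged" (SAP 2.8.3.1). For laboratory data, "if normal ranges are available abnormalities will be flagged" (SAP 2.8.2). Protocol 5.2 uses WHO references for head circumference and malnutrition, but only for eligibility.

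**The concern.** Weight and length are measured at baseline, at eight later core visits and at age 365 days (Protocol Table 8-1). In most safety tables a mean change near zero is reassuring. Here the expected change is positive and depends on age, sex and elapsed time. An infant growing well below the expected rate still contributes a positive raw change.

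A control arm would supply the comparison. In a single-arm trial an external growth standard is the natural substitute, and the visible weight and length text names none. At stake is whether the reader of a safety table, in about 22 infants per cohort, can see slow growth in the weeks after dosing without standardising each listed value by hand.

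**Working it through.** The documents give no figure on weight or length, so there is nothing of the plan's own to reproduce. The check has two parts.

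**Part 1, from the documents.** Elapsed growth time = study day - 1.

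- Day 29 window, Days 23 to 36: 23 - 1 = 22 to 36 - 1 = 35 days; ratio 35/22 = 1.59.
- Day 43 window, Days 37 to 50: 37 - 1 = 36 to 50 - 1 = 49 days; ratio 49/36 = 1.36.
- If SAP 2.8 removes values after Day 43, the second window is 36 to 42 days; ratio 42/36 = 1.17.

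These are window limits. SAP Table 5-2 selects the measurement closest to target, so most values should lie nearer 28 and 42 days.

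Age at the nominal Day 43 visit = entry age + 42 days.

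- Cohort 2 (entry at 1 to 28 days): 43 to 70 days.
- Cohort 1 (entry from 29 days): from 71 days. Protocol 5.1 states no upper age, only body weight below 5 kg. Protocol Table 4-2 models infants of 1 to 7 months, and the visit at 12 months of age implies entry before one year.

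Both sexes are eligible (Protocol 5.1), and the summaries combine them.

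**Part 2, why the sign is uninformative.** Let g be the expected gain in g/day, d the elapsed days, f the fraction of expected gain achieved, and SD the reference standard deviation of weight, held constant over the interval.

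- Raw change = f × g × d.
- Approximate change in z-score = (f - 1) × g × d / SD.

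Raw change is positive for every f above 0. Change in z-score is 0 at f = 1 and negative for every f below 1. This holds whatever g and SD are.

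**Illustration with assumed inputs.** Neither document gives g or SD. Assume g = 15 to 35 g/day, SD = 500 to 800 g, and f = 0.5.

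- Day 29 (d = 28): expected gain 15 × 28 = 420 g to 35 × 28 = 980 g. Raw change is +210 to +490 g. The z-score falls by 210/800 = 0.26 to 490/500 = 0.98.
- Day 43 (d = 42): expected gain 15 × 42 = 630 g to 35 × 42 = 1470 g. Raw change is +315 to +735 g. The z-score falls by 315/800 = 0.39 to 735/500 = 1.47.

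Each z-score range pairs the slowest gain with the widest SD, and the fastest gain with the narrowest. The ranges show what a positive mean can conceal. They do not estimate what will happen in this trial.

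**The case against.** The strongest reply is that nothing in the plan is wrong. Growth is not among the endpoints (SAP Table 1-1), no hypothesis or threshold uses weight, and the dose checks rest on the PK quantities in Protocol 12.5.3 with a safety and efficacy review. Neither document says that a positive mean change shows adequate growth. This stands, and it keeps the point at the level of an improvement to a descriptive table.

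Other replies also stand, in whole or in part:

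- **Slow-growing infants are not hidden.** Every weight is listed by subject, SAP 2.1 gives standard deviation, median, minimum and maximum, and significant examination findings that meet the definition must be recorded as adverse events (Protocol Table 8-2). With about 22 infants per cohort, individual review is feasible. This is partial mitigation: the listing still has to be standardised by hand.
- **Redaction.** Protocol 12.6 is blacked out and the SAP numbering passes from 2.10 to 2.12. A reader might infer that no growth analysis is planned anywhere. The documents do not support that; the point covers only the visible text.
- **Consistency with vital signs.** A reader might infer that the SAP standardises vital signs by age but not weight. It does not. The age-banded limits in SAP Table 5-4 drive flags ("Values below the lower limit or above the upper limit of normal will be listed as Abnormal"), while vital-sign summaries are also raw values and raw changes. Only the laboratory shift tables carry a reference into a summary.
- **Limits of z-scores.** Entry below 5 kg selects older Cohort 1 infants for low weight-for-age, so a stand-alone count below -2 SD would partly reflect eligibility. Gestational age is not among the baseline items in Protocol 8.2, and only Cohort 2 is described as term (Protocol 5), so z-scores at chronological age could misplace a preterm infant. Both points shape the fix.

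**Conclusion.** The point holds as a low-severity improvement. In the visible text, core-period weight and length are summarised only as raw values and raw changes. With growth expected, ages and sexes mixed, windows of 22 to 35 and 36 to 49 elapsed days at their extremes, and no control arm, the sign of the mean change does not show whether infants keep up with expected growth. That conclusion needs only the premise that infants of this age normally gain weight and length.

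Two stronger readings are not supported. The gram and SD figures are not an estimate of the size of the problem, because expected gain, SD and half-rate growth are all assumed. And the gap does not touch the primary artemether Cmax result or the choice of dose, since no stated rule for either uses weight change.

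**What to change.** In SAP 2.8.3.2, keep the raw tables and add WHO sex-specific weight-for-age and length-for-age z-scores, computed at the actual age in days at each measurement. This deals with age mix, sex mix and window width together.

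- **Main growth summary:** within-infant change in z-score from baseline to Day 29 and to Day 43, by cohort and treatment group, with median, minimum and maximum as well as the mean, because a mean alone does not show individual infants crossing centiles.
- **Number (%) below -2 SD:** only as a shift from baseline status, because of the 5 kg entry limit.
- **Footnote:** z-scores use chronological age. Changes may reflect regression to the mean, catch-up growth after malaria or prematurity, and are not evidence of a drug effect.

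The cost is SAP wording, routine programming and a few extra descriptive tables. Age in days, sex, weight and height are already collected (Protocol 8.2 and Table 8-1), so no new data, visits or blood draws are needed.
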